4.2.2 Management of Adverse Events

In case of emergency surgery or if patient develops a serious infection, opportunistic or mycobacterium tuberculosis infections treatment of the infection should be initiated promptly according to local standard of care, during the treatment period, treatment with BI 655064 and SOC will be temporarily interrupted and to be restarted once the patient has recovered as per the investigator's judgement. In addition, patients who develop recurrent infections should have their serum IgM and IgG measured according to investigator's assessment.

In case patient develops a thrombosis suspected to be related to immunosuppression during the treatment period, treatment with BI 655064 and SOC will be temporarily interrupted and anti-thrombotic therapy will be started. Treatment with BI 655064 and/or SOC may be restarted once the patient has recovered according to investigator's assessment.

In case of suspected hepatic injury (as defined in [section 5.2.5.1](#)) during the treatment period, treatment with BI 655064 has to be stopped. If the follow-up identifies a confounder (e.g. high dose of paracetamol) and the liver function has recovered, treatment with BI 655064 may be restarted according to the investigator's assessment after discussion with the sponsor.

In case of severe injection reactions, anaphylactic reactions, cytokine release syndrome, or occurrence of lymphoproliferative diseases, treatment with BI 655064 and SOC will be permanently discontinued and must not be re-introduced.

For side effects known to be related to higher doses of MMF or AZA, dose reduction of MMF or AZA should be considered and handled as per the investigator's judgement.

Malignancies

In case of occurrence of malignant neoplasm other than appropriately treated basal cell carcinoma or squamous cell carcinoma of the skin or in situ carcinoma of uterine cervix, the investigator should discontinue treatment with BI655064. Diagnostics and treatment have to be initiated according to local standard of care.

-in case a patient develops neutropenia (< 1000 cells/ μ l) confirmed by a second measurement consider to reduce or suspend MMF, in case the neutropenia worsens

- In case of emergency surgery during treatment in the study, treatment with BI 655064 and MMF (respectively azathioprine) will be interrupted. Treatment with BI 655064 and SOC will be restarted when the patient has recovered according to investigator's assessment.

- In case of severe injection reactions, anaphylactic reactions or cytokine release syndrome, treatment with BI 655064 and SOC has to be stopped and must not be introduced again.

- In case of occurrence of lymphoproliferative diseases, treatment with BI 655064 and SOC has to be stopped and must not be introduced again.

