Physical examination ⁶	X ^{c1}	X ^t	X ^t	X ^t	X ^t	X ^c	X ^t	X ^t	X ^c	X ^t	X ^t	
12-lead ECG	X ¹			X		X			X			
Lupus PRO, SF-36, FACIT-F, SLEDAI ⁷	X ¹			X		X		X	X			
2 x 24hr urine collection ⁸	X ¹								X			
Pregnancy test ⁹	X ¹	X	X	X	X	X	X	X	X	X	X	
Safety laboratory tests ¹⁰	X ¹	X	X	X	X	X	X	X	X	X	X	
Infection screening ¹¹	X											
Immunology tests ¹²	X ¹			X		X		X	X		X	
██████████				█		█			█		█	
Exploratory biomarker sampling ¹⁴	X ¹	X		X		X			X			
mRNA peripheral blood sampling ¹⁴	X ¹					X			X			
miRNA urine sampling ¹⁴	X ¹					X			X			
██████████	█			█		█			█			
Dispense trial medication and provide instructions for home administration	X	X	X	X	X	X	X	X				
Administer trial medication	X	X	X	X	X	X	X	X				
Continue SOC (MMF or AZA)											▶	
Glucocorticoids tapering ¹⁵									▶			
Compliance Check	X ¹	X	X	X	X	X	X	X	X			
Dispense new diary at baseline and review compliance of diary use	X	X	X	X	X	X	X	X	X			
Adverse events	X ¹⁶	X	X	X	X	X	X	X	X	X	X	
Concomitant Therapy ¹⁷	X ¹⁶	X	X	X	X	X	X	X	X	X	X	

[figure not shown]
FLOW CHART 1 – ROLL-OVER Patients from 1293.10 (Group 1) (CONT)

Vital status collection ¹⁸														X
Completion of patient participation														X

1. Visit 1 must be performed on the same day as the 1293.10 end of treatment (EOT) visit. All assessments performed at the 1293.10 EOT visit will be used as baseline for this trial and should not be repeated. See [Section 6.2.1](#).
2. Any deviation from the visit schedule is strongly discouraged and can only occur with the approval of CTL/CTM. See [Section 6.1](#).
3. For prematurely discontinued patients, an EOT visit should be performed within 7 days of stopping the trial medication and these patients will be invited to attend a subset of follow-up visits. See [Section 6.2.3.3](#).
4. Re-consenting may be necessary when new relevant information becomes available and should be conducted according to the sponsor’s instructions.
5. Previously reported medical history data from 1293.10 will have to be be transcribed into 1293-0013 eCRF. Information on smoking and alcohol history will also be collected if status changed since Visit 1 of 1293.10 trial.
6. Includes height (at screening only), weight and vital signs. X^c is a complete physical examination. X^t is a targeted physical examination. See [Section 5.2.1](#).
7. Questionnaires to be completed at the trial site by the patients before any trial related investigations or discussions. See [Section 5.1.2](#).

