4.2 OTHER TREATMENTS, EMERGENCY PROCEDURES, RESTRICTIONS

4.2.1 Other treatments and emergency procedures

Standard of care (SOC) treatment

All patients will continue to receive SOC treatment for LN of either MMF or AZA in combination with glucocorticoids (if not tapered down to 0mg).

It is acceptable to switch a patient from mycophenolate mofetil to mycophenolate sodium as long as the dose is documented as to mycophenolate mofetil equivalent in the CRF. For simplicity reasons the entire protocol refers to MMF only.

The SOC treatment (MMF and/or AZA) will be procured locally and prescribed at the trial site by the investigator. The sponsor will reimburse the costs for SOC treatment during the trial period in accordance with local regulations.

- MMF and AZA will be considered auxiliary medicinal product (AMP) in this trial. MMF: a stable dose of 1 to 2 g/d. It is recommended not to increase MMF above 2g/d to reduce the risk of MMF related severe side effects. In case of side effects, MMF dose may be reduced to 1g/d; or in case of intolerance, switch to AZA at 2mg/kg/day.

- Patients deviating from the above mentioned dose ranges shall be pre-approved by the CTL/TMM whether they can be enrolled in the trial or not.
- Patients on less than 1g/d MMF before entering the trial may be eligible, if it is documented that the patient did not tolerate higher doses.
- Patients on more than 2g/d MMF before entering the trial may be eligible only if the patient did not suffer from any side effects considered possibly related to MMF in the past.
- AZA: 2mg/kg/day. In case of intolerance or the body weight <50kg, dose may be reduced to 1mg/kg/day or the dosage should be rounded to the nearest 50mg. In regions where only a fixed single dosage is available on the market, the rounding should be done according to the investigators judgment, not exceeding 2mg/kg/day.
- Glucocorticoids: At Visit 1 recommended ≤ 10 mg/d prednisone-equivalent for group 1 patients (depending on actual dose at the end of 1293.10). The tapering of steroids should be performed as follows:
 - Group 1:

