4.2.3 Restrictions

4.2.3.1 Restrictions regarding concomitant treatment

Concomitant medications (or therapy) to provide adequate care may be given as clinically necessary. If a restricted concomitant therapy is required, treatment with trial medication should be permanently discontinued.

Table 4.2.3.1:1 Permitted and restricted medications

Therapy	Treatment Period	Follow up Period
MMF	Permitted if dose $\leq 1-2 \text{ g/d}^*$	Permitted
Azathioprine	Permitted if dose $\leq 2 \text{ mg/kg}$	Permitted
Abatacept or Cyclophosphamide	Not permitted	Not Permitted
Cyclosporine / Tacrolimus / Mizoribine	Not permitted	Permitted if required as per investigator's decision
Belimumab or other "anti- BLYS" or another investigational drug	Not permitted	Not permitted
Biologic B-cell depleting therapy (e.g. anti-CD20)	Not permitted	Not permitted
IV glucocorticoids	Not Permitted	Permitted

¹: for group 1 patients, the doses for MMF and AZA are given in 1293.10 are acceptable to be continued throughout 1293-0013 as long as the patient otherwise qualifies for roll over.

*exception see [section 4.2.1](#).

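### Section 4.2.2 permanently bars MMF/AZA as well as BI 655064 after a severe injection reaction, anaphylaxis or cytokine release syndrome, regardless of cause or recovery

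*Protocol*

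**What the plan says.** Section 4.2.2 of the protocol gives the rule twice. The running text covers severe injection reactions, anaphylaxis, CRS and lymphoproliferative disease in one sentence: "treatment with BI 655064 and SOC will be permanently discontinued and must not be re-introduced". The bullets that close the section repeat it: "treatment with BI 655064 and SOC has to be stopped and must not be introduced again". Neither statement mentions the causal agent, recovery or the trial period. Section 5.2.5.1 sends investigators to 4.2.2 for managing these events of special interest, so this is the operative text.

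Section 4.2.1 glosses SOC treatment as MMF and/or AZA and adds that "MMF and AZA will be considered auxiliary medicinal product (AMP) in this trial". The surgery bullet in 4.2.2 likewise names MMF or azathioprine as the background drug to be interrupted.

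Elsewhere in 4.2.2 the handling is milder. For serious infection and emergency surgery, "treatment with BI 655064 and SOC will be temporarily interrupted and to be restarted once the patient has recovered". For thrombosis, "Treatment with BI 655064 and/or SOC may be restarted once the patient has recovered".

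Table 4.2.3.1:1 marks MMF and azathioprine as permitted in the follow-up period, with no exception for patients stopped under 4.2.2. A footnote says that "the doses for MMF and AZA are given in 1293.10 are acceptable to be continued throughout 1293-0013", provided the patient otherwise qualifies to roll over.

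**The concern.** MMF or AZA is the standard maintenance treatment for these patients. Section 1.3 says that the risk of relapse justifies keeping it going long term. Under 4.2.1, patients with a complete renal response or proteinuria below 0.8 g/d are meant to be off steroids by Week 12 where their condition allows, so MMF/AZA may be the main background immunosuppressant left.

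A reaction to the study injection is a clear reason to stop the study injection. It is not in itself a reason to withdraw a separate oral maintenance drug for good. The rule makes no distinction: a patient who has recovered fully, or who was receiving placebo, is barred from MMF/AZA in the same way as one in whom MMF/AZA was the suspected cause. Because 4.2.2 and the table do not refer to each other, two sites could also treat the same event differently.

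**Working it through.** No figure in the plan bears on this point, so the check sets the texts side by side.

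**Step 1: the rules within 4.2.2.**

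| Event | BI 655064/placebo | MMF/AZA | Condition for restart |
|---|---|---|---|
| Serious, opportunistic or TB infection; emergency surgery | interrupted | interrupted, then restarted | recovery |
| Thrombosis thought to stem from immunosuppression | interrupted, may restart | interrupted, may restart | recovery |
| Suspected hepatic injury | stopped, may restart | not named | confounder found, liver recovered, sponsor consulted |
| Malignancy (listed exceptions apart) | discontinued | not named | none given |
| Severe injection reaction, anaphylaxis, CRS | permanent stop | permanent stop | none allowed |
| Lymphoproliferative disease | permanent stop | permanent stop | none allowed |

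MMF/AZA can therefore resume after events where immunosuppression is itself under suspicion, but never after a reaction to an injection.

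**Step 2: what the protocol links to each trigger.** Section 5.2.5.1 places anaphylaxis under injection reactions, and the scheduled injections are BI 655064 or placebo (4.1.1). Its account of CRS describes immune-cell activation and does not mention MMF or AZA. Lymphoproliferative disease is different: 5.2.5.1 ties that risk to immunosuppression, so stopping both drugs fits and is not questioned here. Section 3.3.4.1 withdraws a patient with anaphylaxis from trial treatment and does not mention SOC. MMF/AZA could still be suspected in an individual case, but the rule does not ask.

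**Step 3: 4.2.2 against Table 4.2.3.1:1.** Two readings would reconcile them.
- The bar might apply only during the treatment period. That would leave it almost without effect. Permanently stopping BI 655064 ends treatment: the EOT visit follows within 7 days (6.2.3.1), and SAP 6.1 starts follow-up the day after the last dose.
- The table might be a general permission, with 4.2.2 as the specific exception. This is the more natural reading. It is also the one under which a recovered patient stays off MMF/AZA.

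Neither section says which is meant.

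**Step 4: size.** The documents give no event rate, and none is assumed here. Section 3.2 reports 20 patients on treatment and 9 in follow-up (20 + 9 = 29) when treatment was unblinded; 4.1.5.1 dates that to 20 October 2020. The current protocol version is dated 21 December 2020. Entry is only from 1293.10, whose final analysis was complete, and Group 2 was cancelled. If no one started treatment after the unblinding, the current text governs new injection reactions in about 20 patients or fewer. Section 4.1.4 notes that patients had already self-injected for a year in 1293.10, which makes new severe reactions less likely.

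**Step 5: efficacy analysis.** A patient with one of these events stops trial medication in any case and falls under the SAP 6.6.1 rules for premature stoppers. Those rules work from the circumstances and renal tests around the stop. Whether MMF/AZA later resumes does not change the planned analysis.

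**The case against.** The strongest reply is that this is a deliberate, conservative safety rule. Its reason may lie in section 1.2, the Investigator's Brochure or the 1293.10 protocol, none of which is in the text reviewed. The entry for 4.2.2 in section 11.2 gives the reasons as guidance to investigators and alignment with 1293.10. That stands as a limit on confidence, but alignment does not explain why MMF/AZA is barred.

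Four stronger readings are tempting, and the documents do not support them.
- *That the protocol contradicts itself.* A reader might infer this from the table, but permitted does not mean that a drug must be resumed after anaphylaxis, and a specific event rule normally overrides a general permission. The footnote concerns doses carried over from 1293.10, not restarting after an event. What remains is an unreconciled tension.
- *That the patient is left without treatment until a flare.* Section 4.2.3.1 says that "Concomitant medications (or therapy) to provide adequate care may be given as clinically necessary". Its table permits IV glucocorticoids in follow-up, and cyclosporine, tacrolimus or mizoribine if the investigator finds them necessary, without requiring a flare. Section 4.2.1 lets patients stay on the lowest workable steroid dose, and the opening of section 8 leaves standard care with the treating physician.
- *That MMF/AZA should simply continue through the event.* Section 5.2.5.1 lists renal and hepatic failure among the complications of CRS, and 4.2.2 interrupts SOC even for serious infection. Default continuation in CRS has no support.
- *That the rule thins out renal monitoring.* The reduced visit schedule in 6.2.3.3 applies to everyone who stops early.

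The placebo case is also smaller than it looks. Allocation was disclosed for the patients remaining in the trial, and SAP 6.6.1 refers to unblinded placebo patients who had approval to stop injecting.

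**Conclusion.** The point holds as a minor patient-safety and consistency matter, worth considering, with medium confidence. The text is unconditional and stated twice, and it is out of line with how 4.2.2 treats other serious events. Read literally, it could take maintenance MMF/AZA from a responder because of a reaction to a different drug or to placebo.

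The practical effect is small, for the reasons of numbers, alternative therapy and analysis already given. The conclusion rests on three assumptions: that SOC in 4.2.2 means MMF/AZA, as 4.2.1 glosses it (another sentence there adds glucocorticoids, which would widen the bar); that 4.2.2 takes precedence over the table; and that no unseen clinical rationale ties MMF/AZA to these three events. A reader might go further and call the rule unsafe or clinically wrong. The documents do not show that.

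**What to change.** In 4.2.2, replace the two statements with one rule for severe injection reaction, anaphylaxis and CRS:
- Stop BI 655064/placebo permanently.
- Hold MMF/AZA during the acute event if clinically indicated, and always in CRS.
- Let MMF/AZA resume after recovery when the investigator judges it appropriate, unless it is a suspected cause.

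Keep the permanent stop of both drugs for lymphoproliferative disease. In Table 4.2.3.1:1, add a cross-reference to 4.2.2 on the follow-up entries for MMF and azathioprine. If the sponsor's clinicians prefer to keep the SOC bar, 4.2.2 should state the reason, and the cross-reference is still needed.

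The cost is a short rewording, one table note and a notice to investigators. The text would depart from 1293.10, and the investigator would have to judge whether MMF/AZA contributed. That is a modest addition: section 5.2.5.2 already asks for causality to trial medication and for possible interactions with an auxiliary medicinal product.

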4.2.3 Restrictions

4.2.3.1 Restrictions regarding concomitant treatment

Concomitant medications (or therapy) to provide adequate care may be given as clinically necessary. If a restricted concomitant therapy is required, treatment with trial medication should be permanently discontinued.

Table 4.2.3.1:1 Permitted and restricted medications

Therapy	Treatment Period	Follow up Period
MMF	Permitted if dose $\leq 1-2 \text{ g/d}^*$	Permitted
Azathioprine	Permitted if dose $\leq 2 \text{ mg/kg}$	Permitted
Abatacept or Cyclophosphamide	Not permitted	Not Permitted
Cyclosporine / Tacrolimus / Mizoribine	Not permitted	Permitted if required as per investigator's decision
Belimumab or other "anti- BLYS" or another investigational drug	Not permitted	Not permitted
Biologic B-cell depleting therapy (e.g. anti-CD20)	Not permitted	Not permitted
IV glucocorticoids	Not Permitted	Permitted

¹: for group 1 patients, the doses for MMF and AZA are given in 1293.10 are acceptable to be continued throughout 1293-0013 as long as the patient otherwise qualifies for roll over.

*exception see [section 4.2.1](#).

4.2.3.2 Restrictions on diet and lifestyle

Patients should not donate blood during MMF treatment and for at least 6 weeks after the last dose of MMF.

In addition, men should not donate semen during MMF/AZA treatment and for at least 90 days after the last dose of MMF/AZA.

During the trial, all patients should avoid intensive physical activity and unprotected exposure to direct sunlight. Intensive physical activity is an activity that is considered as a higher intensity than usually performed by the individual. The use of tanning booths is forbidden.

4.3 TREATMENT COMPLIANCE

Patients must take all doses of trial medication and SOC background therapy according to the trial protocol unless medically indicated. Any temporary interruption should be discussed with the Sponsor and all patients are to be advised of the importance in adhering to the dosing schedule.

Each patient will be provided with a medication bag to store unused and empty cartons of trial medication and a sharp bin to store all used syringes. Patients are requested to bring all remaining trial medication including empty cartons with them when attending onsite visits for compliance checks. At the EOT visit, patients must return the sharp bin to the trial site for disposal in accordance with local requirements.

At each onsite visit, a compliance check of the trial medication will be performed to ensure the weekly injections are being administered correctly at both the trial site and by the patient at home. In case of non-compliance, the site staff will explain to patient the importance of treatment compliance and retrain patient on the injection technique for self-administration at home.

In addition, MMF dosing level will also be checked at the time points indicated in the [Flow Charts](#) to assess compliance. The last two intakes dates and time of MMF taken before the blood sampling will be recorded in eCRF, based on patient's interview.

Any discrepancies should be documented and explained in the eCRF by the investigator or the designee. Patients will also be provided with an e-diary to record the intake of trial medication and SOC background therapy.

The diary is considered to be the primary tool for collecting compliance information to the trial medication.

Patients will be asked to enter date and time of injection as well as the kit number of any dose taken. If a dose was not injected the kit shall still be recorded in the diary

SOC medication is tracked by responding whether the daily medication was taken.

In case the patient did not enter a dose in the diary, the injection shall be entered in the eCRF by the site staff. Proper source documentation will be required for this data entry.

Every kit of investigational product dispensed to a patient should be accounted for (injected or not injected).

5. ASSESSMENTS

5.1 ASSESSMENT OF EFFICACY

5.1.1 Assessment of renal response

For primary, secondary and further efficacy endpoints assessed at baseline and at week 52, the 24hr urine collections will be performed in duplicate (2 x 24hr collection). A detailed description for 24hr urine collection will be provided in the laboratory manual and further instructions will be provided to the patients. For other time points, proteinuria will be assessed by spot urine.

Complete and partial renal responses are defined as follows:

- Complete renal response (CRR) is defined as $U_{\text{prot}} < 0.5$ g/day and **either** eGFR within normal range or decrease in eGFR $< 20\%$ from baseline if below normal range.
- Partial renal response (PRR) is defined as 50% reduction of proteinuria from baseline and **either** eGFR within normal range or decrease in eGFR $< 20\%$ from baseline if below normal range.

An alternative way to calculate CRR and PRR will be to use UP/UC from 24hr urine collections, which could compensate for incomplete urine collections. The decisions which calculation approach is selected for the primary endpoint will be based on review of blinded data before finalization of the TSAP.

A renal flare is defined as follows:

- If proteinuria ≤ 0.5 g/d at baseline: if increase to > 1 g/d (or UP/UC > 1) at anytime during the treatment period as confirmed by a repeat test within 2 weeks and if worsening of proteinuria cannot be explained by any other reasons
Or
- If proteinuria > 0.5 g/d at baseline: if improving to ≤ 0.5 g/d (respectively UP/UC ≤ 0.5) during the treatment period in at least 2 consecutive visits but subsequently increase to > 1 g/d (or UP/UC > 1) as confirmed by a repeat test within 2 weeks and if worsening of proteinuria cannot be explained by any other reasons
Or
- If proteinuria > 0.5 g/d at baseline: if increase to double (respectively UP/UC $> 2x$ baseline) as confirmed by a repeat test within 2 weeks and if worsening of proteinuria cannot be explained by any other reasons
Or
- Decrease in eGFR by $> 20\%$ from baseline and eGFR < 90 ml/min as confirmed by a repeat test within 2 weeks and if worsening of eGFR can not be explained by any other reasons eg, infection or injury.

The primary endpoint is the proportion of patients with complete renal response (CRR) and without any renal flares at week 52.

